Children and young adults will be eligible to participate if they are enrolled in the school, have a formal diagnosis of autism, report no use of micronutrient supplements within the last 3 months, are willing to hold other treatments constant for the 8-week study period, have no major medical problems other than ASD, are willing to provide urine samples, and parents were willing to complete on-line surveys at specified intervals. ASD is defined as being present if the child has a diagnosis from a medical professional trained to diagnose autism, or if the student is determined by school staff and the study psychiatrist to meet *Diagnostic and Statistical Manual of Mental Disorders*, Fourth Edition (*DSM-IV*) criteria for ASD. Informed consent will be obtained from the parent/caregiver of all child study participants and directly from all adult study participants. Adults who are conservated will go through an informed consent process and provide assent, and their conservator will be asked to provide informed consent.

Intervention:

The planned study is open-label and all clinicians, parents, and teachers will be aware of the treatment initiation and duration of 8 weeks. All enrolled children will be provided a micronutrient supplementation (EM Power Plus).

Objectives and outcomes:

The primary goal of the study is to determine if any observed changes in symptoms of ASD are correlated with changes in metabolites that occur during treatment with micronutrients. We hypothesize that micronutrient treatment will lead to changes in physiological pathways and that those changes will correlate with clinical improvements.

The two primary outcome measure is the correlation of the changes in clinical symptoms with the change in specific metabolites. Two measures will be used to assess the change in core and associated features of autism: the Autism Behavior Inventory, Short Form (ABI-S) and the Social Responsiveness Scale (SRS). The ABI-S is an observer-reported outcome scale designed specifically to measure change and severity of ASD symptoms and has been shown to have content validity when completed by caregivers.¹¹ The SRS is one of the most commonly used outcome measures in clinical trials of ASD and focuses on social responsiveness and interaction.¹² Parents/caregivers will be asked to complete both measures at baseline, 4 weeks, and 8 weeks using an on-line and secure platform.

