by automated comparison of ion features to a reference library of chemical standards followed by visual inspection for quality control ¹⁴. For statistical analyses and data display, any missing values will be assumed to be below the limits of detection; these values will be imputed with the compound minimum (minimum value imputation). Data will then be normalized by measured osmolality, which is necessary to reduce the variability ¹⁵. A metabolic pathway for a given metabolite will be assigned based on prior designations in the literature combined with experience from prior datasets at Metabolon.

Statistical methods:

Summary statistics will be used to describe the variables. Change in both the clinical variables and the metabolites will be computed as post-test minus pre-test. Pearson's correlation coefficient will be estimated and tested to index the association between the change in each of the two clinical scales and the change in each metabolite. Given the early-stage nature of the research, we will not adjust for multiple comparisons because we believe it was more important to risk a Type II error than to miss a potentially important signal by being overly conservative, as has been suggested by prior authors ¹⁶.

We define, *a priori*, that a correlation cutoff of an absolute value of ≥ 0.6 is of potential clinical relevance, because, given our planned sample size of 25, we will have approximately 80% power to detect a correlation of that size and such a correlation accounts for roughly one-third of the variance. Others have suggested that correlations with an absolute value of ≥ 0.6 indicate a moderate or higher correlation ¹⁷ (and are hence of greatest interest in pointing to a mechanism of action).

We also plan to examine the number of participants who have a “clinical response,” defined *a priori* as an improvement of 4 or more points in the ABI-S. We will compare the pre-post changes in the ABI-S and SRS in the responder and non-responder groups using the student's t-test.

Planned Data Tables:

Table 1: Characteristics of Enrolled Participants

Category	Characteristic	Subjects N=15	
		%	N
Gender	Male		
	Female		
Ethnicity	White		
	Asian/Pacific Islander		
	No response		
Age	7-10		
	11-14		
	15-21		
	Mean Age		
Primary diagnosis	Autism Spectrum Disorder		
Comorbidities	Intellectual Disability		
	Language Disorder		
	ADHD		
	Pica		
	Global Development Delay		
	Learning Disability		
	Other		
Current meds	Sertraline		
	Lurasidone		

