	Risperidone		
	Birth Control		
	Zonisamide		
	Other		

Table 2: Metabolite correlations

Metabolite	Primary Outcome Measure				Metabolic Pathway
	ABI-S Corr.	p-value	SRS Corr.	p-value	
Amino acids (endogenous)					
Benzene metabolism					
Cholesterol metabolism					
Fatty acids					
Monoterpene phenol					
Neurotransmitters					
Oxidative stress					
Polyol					
Sphingomyelin					
Sugars					
TCA cycle					
Other					

Table 3. Change in outcome scores over the 12-week study period

Outcome Measure	Adjusted Mean Scores (95% CI)			Change from Baseline (95% CI)			
	Baseline	1 month	3 months	1 month	p	3 months	p
Autism Behavior Inventory Total Score							
Social Communication							
Restrictive and Repetitive Behaviors							
Mental Health							
Self-regulation							
Challenging Behaviors							
Social Responsiveness Scale Total Score							
Awareness							
Cognition							
Communication							
Mannerisms							
Motivation							

Mean change scores will be adjusted for age and gender; *indicates statistically significant change from baseline

REFERENCES:

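### The unadjusted primary screen labels |r| ≥ 0.6 as relevant, but nothing planned shows how many such hits chance alone would give

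*Combined protocol and SAP*

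**What the plan says.** The Objectives and outcomes section makes the correlation between symptom change and metabolite change the primary outcome. It speaks of particular metabolites but names none. The Statistical methods section sets the scope: Pearson's correlation will be estimated and tested for "the association between the change in each of the two clinical scales and the change in each metabolite". On multiplicity it says "we will not adjust for multiple comparisons because we believe it was more important to risk a Type II error", giving the early stage of the work and a published argument against adjustment as reasons.

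The same section declares in advance that "a correlation cutoff of an absolute value of ≥ 0.6 is of potential clinical relevance". Three reasons are given for 0.6:

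- power: "given our planned sample size of 25, we will have approximately 80% power to detect a correlation of that size";
- variance explained, put at about a third;
- a published guide: "Others have suggested that correlations with an absolute value of ≥ 0.6 indicate a moderate or higher correlation".

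The results go into a shell titled "Table 2: Metabolite correlations", with a correlation and a p-value for each scale and a pathway column. The shell does not say whether every metabolite will be listed or only those that reach the cutoff. The documents give no number of metabolites, no significance level, no expected count under the null, and no permutation or other screen-wide reference.

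**The concern.** All three reasons for 0.6 concern a single correlation: how likely a true one is to be found, how much variance it explains, and what size others call moderate. None says how often chance reaches 0.6 when two scales are run against a whole metabolite panel.

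The result of such a screen is a list of hits, and the plan regards those hits as the ones of most interest for mechanism. A reader shown, say, three metabolites above 0.6 on one scale will want to know whether three is more than chance would give. The answer depends on the number of metabolites tested and the number of participants analysed. It also depends on how strongly the metabolites are correlated with one another. The plan commits to reporting none of these. The per-test p-values remain informative, but they do not settle the question for the list.

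**Working it through.** **Inputs from the documents:** planned n = 25, cutoff 0.6, two scales, stated power of about 80% (all Statistical methods).

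**Assumptions, because the documents are silent:** number of metabolites M = 100, 200, 500 or 1,000; two-sided level 0.05 for the power check; n = 20 as an example of a smaller analysed sample, since no dropout allowance is stated. The Table 1 shell shows 15 subjects; that value is carried only to show sensitivity.

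**1. The plan's own figure.** By Fisher's z, power = Φ(atanh(0.6)·√(n−3) − 1.960). At n = 25 this is Φ(0.693 × 4.690 − 1.960) = Φ(1.291) = 0.90; simulation of the t-test gives 0.91. The stated 80% does not reproduce at two-sided 0.05. It corresponds to n of about 19 to 20, or at n = 25 to a two-sided level of about 0.016. This does not affect the present point, because power describes a single test when the true correlation is 0.6 and says nothing about null hits. The variance figure is 0.6² = 0.36, consistent with the text.

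**2. Null probability for one test.** With normal data and no association, t = 0.6·√(n−2)/√(1−0.36) on n−2 degrees of freedom, two-sided:

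- n = 25: t = 0.6 × √23 / 0.8 = 3.597, p = 0.00152
- n = 20: t = 0.6 × √18 / 0.8 = 3.182, p = 0.00516 (3.4 times the n = 25 value)
- n = 15: t = 0.6 × √13 / 0.8 = 2.704, p = 0.01805 (11.9 times)

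**3. Expected chance hits over both scales** = 2M × p. This expectation holds whether or not the tests are independent.

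| M (assumed) | Tests | n = 25 | n = 20 (assumed) | n = 15 (Table 1 shell) |
|---|---|---|---|---|
| 100 | 200 | 0.3 | 1.0 | 3.6 |
| 200 | 400 | 0.6 | 2.1 | 7.2 |
| 500 | 1,000 | 1.5 | 5.2 | 18.1 |
| 1,000 | 2,000 | 3.0 | 10.3 | 36.1 |

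**4. Spread around the expectation at n = 25.** This does depend on correlation among metabolites. A simulation with assumed blocks of 20 metabolites correlated at 0.5 gave, per scale:

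| M (assumed) | Mean | 95th percentile | P(at least 1) | P(3 or more) |
|---|---|---|---|---|
| 100 | 0.16 | 1 | 12% | 0.7% |
| 200 | 0.31 | 2 | 22% | 1.9% |
| 500 | 0.76 | 3 | 46% | 6.8% |
| 1,000 | 1.53 | 4 to 5 | 71% | 21% |

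At the planned n, three hits on one scale would therefore stand out with 200 metabolites and would be unremarkable with 1,000. The planned reporting does not tell the reader which case applies.

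**The case against.** The best defence is that the plan is open about what it does. It calls the research early-stage, gives a reason and a citation for not adjusting, and describes its label in terms of potential. At n = 25 the cutoff is itself strict: a p-value of about 0.0015 is roughly 33 times smaller than 0.05 (0.05 / 0.00152 = 33). Table 2 prints a p-value beside each correlation, and once M and n are known the expected count is one multiplication. All of this stands. It limits the point to a reporting addition and rules out treating non-adjustment as a fault. The defence does not supply M or the analysed n, and the multiplication gives only the mean of the chance count, not its spread under correlated metabolites.

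Three stronger readings are tempting, and the documents do not support them.

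- **That chance would flood the list.** A reader might infer this from the n = 15 column. The only stated planned sample size is 25; 15 appears only in an empty table shell. The Background reports fifteen children in the investigators' own sulforaphane trial, and the Table 3 shell also departs from this protocol (12 weeks against 8). Carry-over from another document is plausible, though not proven. The 15 and 25 must be reconciled, but as a separate matter.
- **That the screen cannot address its primary question at all.** This is too strong, because per-test correlations and p-values are planned.
- **That 10 to 100 false findings should be expected.** That is 2M × 0.05 for the assumed range of M. The plan states no significance level and attaches its label to 0.6, so this is not the count the plan defines.

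The absence of a control group ("The planned study is open-label"; "All enrolled children will be provided a micronutrient supplementation") limits causal interpretation of any hit. It is a different issue from chance hits and does not carry this point.

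**Conclusion.** The point holds as a modest, cheaply closed gap in how the primary outcome will be reported. The screen is unadjusted by a disclosed and defensible choice, but no screen-wide chance reference accompanies the 0.6 label.

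At the planned n of 25 the expected number of chance hits over both scales runs from 0.3 to 3.0 for an assumed 100 to 1,000 metabolites. It is below one at 100 to 200. It rises with more metabolites, and by a factor of 3.4 if 20 rather than 25 are analysed.

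These figures rest on a global null, normal data and assumed values of M; the percentiles also rest on an assumed block correlation. The normal-theory probability is approximate here. The plan imputes missing values at the compound minimum and states no transformation, and heavy tails in both changes would raise the chance rate. A permutation reference needs neither normality nor an assumed M or correlation structure.

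The stated rationale also names the wrong error: missing a signal is the Type II error, and not adjusting risks Type I. This is a wording slip that changes no analysis.

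**What to change.** Keep the non-adjustment, the raw p-values and the 0.6 label. Report with Table 2:

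1. the number of metabolites tested and the number of participants analysed;
2. for each scale, the observed count of |r| ≥ 0.6 beside the mean and 95th percentile of its permutation distribution at the analysed n. Shuffle participants' clinical change scores, keeping the two scales paired, against the intact metabolite matrix, so that correlation among metabolites and between scales is preserved.

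State in advance that the comparison is context and not a pass/fail test. Benjamini-Hochberg q-values are optional, since the plan declined adjustment with reasons. As wording only, change the rationale to say that the plan accepts the risk of a Type I error.

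The cost is a few lines of code and a table footnote, with no change to design or data collection. The downside is that the report may have to say that the hits do not exceed chance. It should then add that a count within the chance range is not proof of no correlation, because the count has low power when few metabolites are truly associated.

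### The stated 80% power for a correlation of 0.6 with 25 participants does not reproduce (about 91%), and it does not describe the 0.6 cutoff it is used to support (about 53%)

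*Combined protocol and SAP*

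**What the plan says.** The Statistical methods section of the combined protocol and SAP tests Pearson correlations between the change in each of two clinical scales (ABI-S and SRS) and the change in each metabolite, without multiplicity adjustment. These correlations are the primary outcome. It sets in advance that "a correlation cutoff of an absolute value of ≥ 0.6 is of potential clinical relevance" and gives three reasons:

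- Power: "given our planned sample size of 25, we will have approximately 80% power to detect a correlation of that size".
- Variance explained: "such a correlation accounts for roughly one-third of the variance".
- A cited convention for grading the strength of a correlation.

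The same section says the investigators do not want to "miss a potentially important signal by being overly conservative". It does not state alpha, sidedness or an allowance for lost pairs. The shell titled "Table 2: Metabolite correlations" has a correlation and a p-value for each scale, but no interval. The shell for Table 1 is headed with 15 subjects, not 25.

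**The concern.** Two things look wrong. First, 80% is too low for a true correlation of 0.6 with 25 pairs at the usual two-sided 5% level. Second, the power of a test against zero correlation is offered as a reason for a cutoff on the observed correlation, and these are different events. At 25 pairs the test rejects from an observed value of about 0.40, while the cutoff asks for 0.60.

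What is at stake is how the primary results are read. A reader may take 80% as the chance that a metabolite with a true correlation of 0.6 is marked as potentially relevant. If the real chance is near one half, a correlation below the cutoff says little against a mechanism, which matters in a study that says it wants to avoid missing signals.

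**Working it through.** **Inputs.** From Statistical methods: n = 25, true correlation 0.6, stated power about 80%, cutoff 0.6 on the absolute observed correlation, Pearson test, no multiplicity adjustment. Assumed because not stated: two-sided alpha of 5% (other values shown), 25 complete pairs, bivariate normal changes.

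**1. Attempt to reproduce the 80%.** By Fisher's z, power is approximately Φ(atanh(0.6) × √(n − 3) − 1.960), where the opposite tail is negligible. With n = 25 this is Φ(0.693 × 4.690 − 1.960) = Φ(1.291) = 90.2%.

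For the exact figure, the critical t on 23 degrees of freedom is 2.069, so the critical correlation is 2.069/√(2.069² + 23) = 0.396. Integrating the exact density of the sample correlation beyond ±0.396 gives 91.3%, and simulation agrees (91.3%).

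| Test, n = 25, true r = 0.6 | Fisher z | Exact |
|---|---|---|
| One-sided 5% | 94.6% | 95.3% |
| Two-sided 5% | 90.2% | 91.3% |
| Two-sided 2.5% | 84.4% | 85.7% |
| Two-sided 2% | 82.2% | 83.6% |
| Two-sided 1% | 75.0% | 76.2% |

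**2. What would give 80%.** Any one of these would, with the other inputs held:

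- a two-sided alpha of about 0.014;
- a true correlation of about 0.53 (0.526 exact, 0.535 Fisher z);
- 18 to 19 complete pairs at two-sided 5% (79.0% at 18, 81.4% at 19), a loss of 6/25 = 24% to 7/25 = 28%.

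The document states none of them.

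**3. What the cutoff does.** An observed 0.6 at n = 25 has t = 0.6 × √(23/0.64) = 3.60, p = 0.0015. From the exact density:

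- The probability that the observed absolute value is at least 0.6, given a true 0.6, is 52.5%.
- The probability that p<0.05 but the absolute value is below 0.6 is 91.3% − 52.5% = 38.8%.
- Retention of 80% needs a true correlation of about 0.69.
- Sample size barely matters for a true 0.6: retention is 53.3% at n = 15 and 52.8% at n = 20.

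**4. Precision of an observed 0.6.** The 95% interval on the z scale is 0.693 ± 1.960/4.690 = 0.275 to 1.111. Back-transformed, it is 0.27 to 0.80.

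**5. Null pairs.** With no true correlation, p<0.05 flags 5% of pairs and the cutoff flags 0.152%, a ratio of 0.05/0.00152, about 33.

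**6. If Table 1's 15 is the real number.** Power at a true 0.6 is 70.1% two-sided 5% and 80.6% one-sided 5%. The one-sided case does return 80%, but nothing in the document says the figure came from there, and the sentence names 25.

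**The case against.** The strongest reply has four parts.

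*Alpha is not stated, so the provable defect is a missing input.* Two-sided 2% and 1% bracket 80%, and an unstated dropout allowance would also explain it. This is fair as far as it goes. But the sentence ties the figure to the planned 25, the plan declines multiplicity adjustment (so a reduced alpha is unlikely), and neither explanation changes the 53%.

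*The 91% assumes normality.* The plan correlates raw changes, mentions no log transformation, and imputes missing values at the compound minimum. Simulations with metabolite change as a difference of lognormals gave power anywhere from 68% to 91%, depending on the assumed log-SD and on how the change was constructed. In the least favourable version, retention fell from 51% to 32% as skew rose. This part stands: the replacement text should carry the normality condition. It does not rescue the 80%, because the plan makes no such allowance, and skew makes the cutoff's retention worse.

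*The 53% is nearly automatic.* An almost unbiased estimate exceeds its own true value about half the time, and the plan never says 80% is the chance of meeting the cutoff. Both are true. They also show why test power is no reason for placing the cutoff at 0.6.

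*Little harm follows.* The error is conservative, and p-values appear in Table 2 anyway, so significant correlations below 0.6 would be visible. This limits the severity. Adding intervals is good practice and not strictly a correction.

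**Conclusion.** The concern holds and should be fixed, though it is not fatal. With 25 complete pairs, a two-sided 5% test and approximate bivariate normality, power at a true 0.6 is about 91%, so the implied type II error is about 9% and not 20%. On that reading the study has more power than it claims.

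The mismatch with the cutoff is the more important part and does not depend on alpha: under normality a true 0.6 meets the 0.6 rule about 53% of the time. The power statement should therefore not be used to support the rule. The other two stated grounds are untouched: 0.6² = 0.36 is indeed roughly one third of the variance, and the convention is a matter of choice. The 15 against 25 discrepancy is a separate editorial point, but it needs an answer because at 15 the two-sided power would be about 70%, below the stated figure.

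**What to change.** 1. State alpha, sidedness, the number of complete pairs assumed and the distributional assumption.
2. Replace the power statement with, for example: *Assuming approximate bivariate normality, 25 complete pairs and a two-sided 5% test, power is about 91% for a true correlation of 0.6 and 80% for about 0.53. The 0.6 cutoff retains a true correlation of 0.6 with probability about 53%, and a true 0.69 with probability about 80%.* If a loss of pairs was intended, say so and recompute.
3. Drop power as a reason for the cutoff and keep 0.6 on its other two grounds. Do not swap it for p<0.05, which would flag about 33 times as many null pairs.
4. Add a 95% confidence interval beside each correlation in Table 2, so that a value below 0.6 is not read as absence of association.
5. Reconcile the Table 1 heading of 15 with the planned 25. If 15 is meant, state about 70% power (two-sided 5%).

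The cost is a few sentences, one interval for each of the two correlations per row in Table 2, and one table heading. The test's power figure improves and the figure quoted for the cutoff becomes less favourable. No participants, data or screening rule change.

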Since micronutrient deficiencies are common in children with ASD, and because there is scientific evidence to suggest that supplementation may produce important clinical benefits, we seek to more precisely examine the mechanism of action of micronutrient supplementation through a clinical trial using comprehensive, before-and-after metabolomic analyses. Since the prior study, the metabolomics field has advanced so that it is now possible to obtain metabolomic analyses using Dried Blood Spots (DBS), which are minimally invasive (requiring only a fingerstick and a drop of blood), and provide a much broader metabolomic analysis than urine. We therefore plan to use this new technology in the current study. The analyses may suggest specific metabolic changes that underlie clinical improvements in ASD, which may provide a greater understanding of the physiology of ASD and lead to improved, targeted treatment options.

Methods:

Approvals: The clinical trial will be reviewed and approved by the UCSF Committee on Human Research prior to performing any study activities. The study protocol will be registered at clinicaltrials.gov.

Participants: The UCSF investigative team has an ongoing relationship with a local, non-public school (Oak Hill School, San Anselmo, CA) that specializes in the education of children and young adults with autism and related neurodevelopmental disorders (ages 5-22, grades K-12). This unique academic-school-parent partnership was created with the goal of improving overall care and communication between caregivers, clinical providers, and teachers. All children/families attending the school (n=50 currently) will be invited to participate in the study through e-mail, informational flyers, and an evening informational session.

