Dried blood spots (DBS) will be collected on the day of study initiation and on the final day of the study after the 8-week treatment period. We will be using “batch enrollment” where the parents and caregivers of all potentially eligible participants will be screened for eligibility and asked to go through an informed consent process. Once the final “set” of eligible student participants is identified, they will all be given the study medication and have the DBS sample collected on the same day. DBS is collected using a simple, sterile, finger-prick device and technique, which generates a drop of blood. The participant will be assisted to place his/her finger on a special DBS “card” which will collect the drop of blood. DBS cards will be individually packaged and stored immediately at -80 °C. During the screening visit, children will have a brief physical examination including height and weight to guide the proper dosing. Micronutrient treatment will be provided at the screening visit along with dosing instructions, but participants will not begin the treatment until the study initiation day, when the DBS samples are collected.

Safety assessments:

Parents/caregivers and teachers will be advised to report any concerns about a new medical problem immediately to the study investigators, who will be available at all times to receive reports of possible adverse effects. At the 4 week and 8-week on-line questionnaires, parents/caregivers will be asked to report any new medical problems or concerns for possible side effects.

Metabolomic analyses:

All DBS samples will be sent on dry ice in one batch to Metabolon (Morrisville, NC). Metabolomics analyses will be conducted at Metabolon as previously described ¹³. Briefly, samples will be subjected to methanol extraction, then split into five aliquots for analysis by ultrahigh performance/mass spectrometry in the positive (two methods), negative or polar ion modes. Metabolites will be identified

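### The plan gives 25 as its sample size in the power statement and 15 in the Table 1 shell, and the stated power of about 80% for r = 0.6 matches neither (about 91% at 25, about 70% at 15)

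*Combined protocol and SAP*

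**What the plan says.** The Statistical methods section plans a Pearson correlation between the change in each metabolite and the change in each of the ABI-S and the SRS: "correlation coefficient will be estimated and tested to index the association between the change in each of the two clinical scales". It adds that "we will not adjust for multiple comparisons". It then declares that "a correlation cutoff of an absolute value of ≥ 0.6 is of potential clinical relevance". The first reason given for 0.6 is power: "given our planned sample size of 25, we will have approximately 80% power to detect a correlation of that size". Two further reasons follow, the share of variance explained and a published convention for grading correlations.

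The section states no alpha level, no sidedness, no dropout allowance, and no distinction between participants enrolled and pairs analysed.

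The next section, Planned Data Tables, opens with the Table 1 shell for enrolled participants, whose column header gives N as 15. The Table 2 shell has a correlation and a p-value for each scale, but no place for the number of pairs or for a confidence interval.

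The Background describes an earlier sulforaphane study that enrolled fifteen children.

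**The concern.** The number of complete before-and-after pairs fixes two things on which the plan relies: the power of each correlation test, and how often an absolute correlation of 0.6 arises by chance. The plan prints two values for that number and supports its cutoff by a power figure tied to one of them.

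If the power figure is wrong for its own sample size, part of the printed justification for 0.6 goes with it. If the trial were to run at 15, a metabolite flagged at 0.6 would be much weaker evidence than the same flag at 25. With no multiplicity adjustment, the cutoff is the main filter on the primary outcome, so readers need to know its properties at the size actually used.

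**Working it through.** **Inputs from the plan.** Sample size 25 (Statistical methods) or 15 (Table 1 header); r = 0.6; power about 80%; Pearson test.

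**Assumptions.** Two-sided alpha 0.05, because the cutoff is on the absolute value; bivariate normal changes. Other alphas and a one-sided test are tried below.

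**1. Reproducing the plan's figure at 25.** By the Fisher z approximation, power = Φ(atanh(r)·√(n−3) − z), with atanh(0.6) = 0.693 and z = 1.960:

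- n = 25: 0.693 × √22 − 1.960 = 1.29, so power is 90.2%.
- The distribution of r simulated under bivariate normality (1,000,000 draws), with the t-based critical value, gives 91.3%.

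The 80% does not reproduce. Other settings at n = 25 (Fisher z, then simulation, where two figures are given):

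- one-sided 5%: 94.6% to 95.3%
- two-sided 2.5%: 84.4% to 85.7%
- two-sided 1%: 75.0% to 76.2%
- r = √(1/3) = 0.577 (exactly one-third of the variance), two-sided 5%: 87.0% to 88.4%

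Reaching 80% at 25 needs an unstated alpha near 0.017 (Fisher z 80.5%), or a true r near 0.535 at 5%.

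**2. Where 80% does fit.** n = ((1.960 + 0.842)/0.693)² + 3 = 19.3. By simulation, 18 pairs give 79.0% and 19 give 81.4%. The same formula for 90% power gives 24.9, so 25 is the size for 90%, not 80%.

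**3. Power at 15.** 0.693 × √12 − 1.960 = 0.44, so Fisher z power is 67.0%; simulation gives 70.1%. A one-sided 5% test gives 77.5% (Fisher z) or 80.6% (simulation), so 80% fits 15 only under a one-sided test that the plan does not state.

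**4. The cutoff, as distinct from the test.** With no true association, t = 0.6·√(n−2)/√(1−0.36):

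- n = 15: t = 2.704 on 13 df, two-sided probability 0.01805
- n = 25: t = 3.597 on 23 df, two-sided probability 0.00152
- ratio: 0.01805/0.00152 = 11.9

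The plan gives no metabolite count. If 500 metabolites were tested on two scales and none were truly associated, expected chance flags would be 1,000 × 0.00152 = 1.5 at 25 and 1,000 × 0.01805 = 18 at 15. For 200 to 1,000 metabolites the ranges are 0.6 to 3.0 and 7 to 36.

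When the true r is 0.6, the observed absolute r reaches 0.6 in 53.3% of simulated samples at 15 and 52.4% at 25. The critical absolute r for p < 0.05 is 0.514 at 15 and 0.396 at 25, both below 0.6. The cutoff is therefore stricter than the test, and the quoted power describes the test.

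**5. Summary** (two-sided 5%, simulated power)

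| Complete pairs | Power of p < 0.05 test at r = 0.6 | Chance of abs. r ≥ 0.6, no association | Chance of abs. r ≥ 0.6, true r = 0.6 | 95% CI at observed r = 0.60 |
|---|---|---|---|---|
| 15 | 70% | 1.8% | 53% | 0.13 to 0.85 |
| 25 | 91% | 0.15% | 52% | 0.27 to 0.80 |

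The intervals are tanh(0.693 ± 1.960/√(n−3)).

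**The case against.** The two sizes do not have equal standing. Only 25 is declared as planned, in a sentence that uses it. The 15 heads an empty shell, and the shells look reused: an earlier study had fifteen children, Table 1 already names particular drugs, and Table 3 is titled for 12 weeks in an 8-week trial. If the 15 is a leftover, the loss of power and the 12-fold chance rate do not arise. This is a fair inference, and the likeliest remedy is a corrected header. It remains an inference, and it leaves the mismatch between 80% and 25 untouched.

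The sponsor might say that 80% silently allows for attrition: 25 enrolled and 19 complete pairs would be a loss of 6/25 = 24%. But the sentence ties 80% to 25, and no dropout rate appears.

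Table 2 would print p of about 0.018 for r = 0.6 at 15 pairs and about 0.0015 at 25, so the weaker evidence would be visible in part. The cutoff also rests on two reasons that do not depend on sample size. Both points stand and limit the harm.

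A reader might infer that power drops from 80% to 70%. That sets the plan's figure beside one computed on another basis. On one basis the change is from 91% to 70%; if 80% at 25 is taken as true through an alpha near 0.017, power at 15 is about 50%. None of the settings tried gives 80% at 25 together with 70% at 15.

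A reader might also infer that 25 cannot be recruited, since "All children/families attending the school (n=50 currently) will be invited to participate" and there is a single batch. The plan gives no uptake, eligibility or attrition figure, and 25 of 50 is not shown to be out of reach.

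**Conclusion.** The point holds as an inconsistency and an arithmetic error, not as a demonstrated power shortfall. The plan prints 25 and 15 without reconciling them, and its 80% matches neither under a two-sided 5% Pearson test with bivariate normal changes. At the declared size of 25 the plan understates its power by about 11 points (91% against 80%); at 15 it would overstate it by about 10 (70% against 80%).

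Separately, the power figure is offered in support of the 0.6 cutoff but does not describe it. The cutoff detects a true r of 0.6 only about half the time at either size. What changes between the sizes is its chance rate, by a factor of about 12.

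The conclusion depends on the assumed alpha and sidedness, which the plan does not state. The documents do not support reading the Table 1 header as a second enrolment target, nor concluding that the trial will be underpowered.

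**What to change.** 1. Make the two sizes agree. Correct the Table 1 header to 25 or, if 15 is the real target, change the sample size in Statistical methods.
2. State alpha and sidedness for the correlation tests.
3. Replace the approximate 80% with the figure for the chosen number of complete pairs: on a two-sided 5% basis, about 91% at 25, 81% at 19 and 70% at 15. Say that it refers to the p < 0.05 test.
4. State the cutoff's chance rate at that number (0.15% per test at 25, 1.8% at 15) and that a true r of 0.6 reaches it only about 53% of the time.
5. In Table 2, print the number of pairs analysed and a 95% CI for each correlation. Power recomputed after the data is not a substitute.

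The cost is wording and one recalculation, plus extra columns in Table 2; no participants or procedures are added. The downside is that the stated power becomes less favourable if 15 is the real target; at 25 it becomes more favourable.
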